8.3 EFFICACY CRITERIA FOR TUMOR RESPONSE

EVALUATION OF NEW LESIONS

The finding of a new lesion should be unequivocal (i.e. not due to difference in scanning technique, imaging modality, or findings thought to represent something other than tumor). However, a lesion identified on a follow-up scan in an anatomical location that was not scanned at baseline is considered new and will indicate progressive disease (PD). If a new lesion is equivocal (because of small size etc.), follow-up evaluation will clarify if it truly represents new disease and if PD is confirmed, progression should be declared using the date of the initial scan on which the lesion was discovered.

8.4 EVALUATION OF SURVIVAL

Overall Survival: Overall Survival (OS) is defined as the time from start of TTFields therapy (Day 1) to death due to any cause, or last follow-up at 60 months.

8.5 RESPONSE REVIEW

Response assessment will be determined by the investigator.

9. SAFETY

9.1 SPECIFICATION OF SAFETY PARAMETERS

The Investigator is responsible for monitoring the safety of participants who have enrolled in the study. Safety assessments will be based on medical review of adverse events and the results of safety evaluations at specified time points as described in Section 7.8, Schedule of Events. Any clinically significant adverse events persisting at the end of treatment visit will be followed by the Investigator until resolution/stabilization or death, whichever comes first.

9.2 DEFINITIONS

ADVERSE EVENT (AE)

An adverse event is defined as any undesirable physical, psychological or behavioral effect experienced by a participant during their participation in an investigational study, in conjunction with the use of the investigational product, whether or not considered intervention-related (21 CFR 312.32 (a)). In general, this includes signs or symptoms experienced by the participant from the time of signing the informed consent to completion of the study.

AEs may include, but are not limited to:

- Subjective or objective symptoms spontaneously offered by the participant and/or observed by the Investigator or medical staff.
- Clinically significant laboratory abnormalities.
- A significant worsening of the participant's condition from study entry.
- Disease signs and symptoms and/or laboratory abnormalities existing prior to the use of the study treatment that resolve but then recur after treatment.
- Disease signs and symptoms and/or laboratory abnormalities existing prior to the use of the study treatment which increase in frequency, intensity, or a change in quality after treatment.

SERIOUS ADVERSE EVENT (SAE)

An AE or suspected adverse reaction is considered "serious" if, in the view of either the Investigator, it results in any of the following outcomes:

- Death,
- A life-threatening adverse event,
- In-patient hospitalization or prolongation of existing hospitalization,
- A persistent or significant incapacity or substantial disruption of the ability to conduct normal life functions, or
- A congenital anomaly/birth defect.

Important medical events that may not result in death, be life-threatening, or require hospitalization may be considered serious when, based upon appropriate medical judgment, they may jeopardize the participant and/or participant may require medical or surgical intervention to prevent one of the outcomes listed in this definition. Examples of such medical events include:

- Allergic bronchospasm requiring intensive treatment in an emergency room or at home,
- Blood dyscrasias or convulsions that do not result in in-patient hospitalization, or

- The development of drug dependency or drug abuse.

UNANTICIPATED PROBLEMS (UP)

The Office for Human Research Protections (OHRP) considers UPs involving risks to participants or others to include, in general, any incident, experience, or outcome that meets all of the following criteria:

1. Unexpected in terms of nature, severity, or frequency given (a) the research procedures that are described in the protocol-related documents, such as the IRB-approved research protocol and informed consent document; and (b) the characteristics of the participant population being studied;
2. Related or possibly related to participation in the research (“possibly related” means there is a reasonable possibility that the incident, experience, or outcome may have been caused by the procedures involved in the research); and
3. Suggests that the research places participants or others at a greater risk of harm (including physical, psychological, economic, or social harm) than previously known or recognized.
4. This definition could include an unanticipated adverse device effect, any serious adverse effect on health or safety or any life-threatening problem or death caused by, or associated with, a device, if that effect, problem, or death was not previously identified in nature, severity, or degree of incidence in the investigational plan or application (including a supplementary plan or application), or any other unanticipated serious problem associated with a device that relates to the rights, safety, or welfare of participants (21 CFR 812.3(s)).

This study will use the OHRP definition of UP.

SEVERITY OF EVENT

The Investigator will grade the severity of each AE using, when applicable, the current version of the [CTCAE v5.0](#). In the event of an AE for which no grading scale exists, the Investigator will classify the AE as defined below:

- **Mild** (grade 1) – An event that is usually transient in nature and generally not interfering with normal activities
- **Moderate** (grade 2) – An event that is sufficiently discomforting to interfere with normal activities
- **Severe** (grade 3) – An event that is incapacitating with inability to work or do usual activity, or inability to work or perform normal daily activity
- **Life-threatening/debilitating** (grade 4) – An event that puts the participant at immediate or potential risk of death, requires hospitalization, or which drastically impacts a participant’s well-being
- **Fatal** (grade 5)

ASSESSMENT OF CAUSALITY RELATIONSHIP TO OPTUNE® DEVICE

For all collected AEs, the clinician who examines and evaluates the participant will determine the AE’s causality based on temporal relationship and his/her clinical judgment. The degree of certainty about causality will be graded using the categories below.

- **Definite** – The AE is clearly related to the study treatment.
- **Probable** – The AE is likely related to the study treatment.

- *Possible* – The AE may be related to the study treatment.
- *Unlikely* – The AE is doubtfully related to the study treatment.
- *Unrelated* – The AE is clearly NOT related to the study treatment.

Per 21 CFR 803.3, Medical Device Reporting: the definition of caused or contributed means that a death or serious injury was or may have been attributed to a medical device, or that a medical device was or may have been a factor in a death or serious injury, including events occurring as a result of:

1. Failure
2. Malfunction,
3. Improper or inadequate design
4. Manufacture
5. Labeling, or
6. User error.

9.3 EXPECTEDNESS

The Principle Investigator will be responsible for determining whether an AE is expected or unexpected. An AE will be considered unexpected if the nature, severity, or frequency of the event is not consistent with the risk information previously described for the study agent.

9.4 ADVERSE EVENT LIST(S)

ADVERSE EVENT LIST FOR TT FIELD THERAPY WITH OPTUNE® DEVICE

Detailed information about the risks and expected AEs associated with using the Optune® may be found in the current edition of the manufacturer's Patient Information and Operation Manual. The most frequent adverse reactions associated with use of Optune® device is dermatitis.

9.5 ADVERSE EVENT ASSESSMENT AND FOLLOW-UP

The occurrence of an UP, AE or SAE may come to the attention of study personnel during study visits and interviews of a study participant presenting for medical care, or upon review by a study monitor. All AEs including local and systemic reactions not meeting the criteria for SAEs will be captured on the appropriate CRF. Information to be collected includes event description, time of onset, clinician's assessment of severity, seriousness, expectedness, relationship to study product (assessed only by those with the training and authority to make a diagnosis), and date of resolution/stabilization of the event. All AEs occurring while on study must be documented appropriately regardless of relationship. All AEs will be followed to adequate resolution.

Any medical condition that is present at the time that the participant is screened will be considered as baseline and not reported as an AE. However, if the study participant's condition deteriorates at any time during the study, it will be recorded as an AE.

Changes in the severity of an AE will be documented to allow an assessment of the duration of the event at each level of severity to be performed. AEs characterized as intermittent require documentation of onset and duration of each episode.

At each study visit, the Investigator will inquire about the occurrence of AE/SAEs since the last visit. Events will be followed for outcome information until resolution or stabilization.

The Investigator will record all reportable events with start dates occurring any time after informed consent is obtained until 7 (for AEs) or 30 days (for SAEs) after the last day of study participation or until the participant receives alternative therapy for his/her SCLC, whichever occurs first. Any SAE that occurs after treatment with alternative therapy will be reported only if the Investigator or current treating physician has assessed the SAE as related to the study treatment. Adverse events will be evaluated using the current version of the [CTCAE v5.0](#).

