7.5 END OF TREATMENT VISIT

The end of treatment (EOT) visit should be conducted 10 \pm 10 days following completion of TTField therapy. All AEs that occur prior to the EOT visit should be recorded. Participants with an AE of Grade > 1 will be followed until the resolution of the AE to Grade 0-1 or until the beginning of a new anti-cancer therapy, whichever occurs first. Imaging (CT and/or MRI as appropriate) will be used to assess disease staging.

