^DInitial imaging at screening must be within 12weeks prior to the first dose of TTField therapy. Scans performed as part of routine clinical management are acceptable for use as the screening scan if they are of diagnostic quality and performed within 12 weeks prior to the first dose of trial treatment. Measurable disease based on RECIST 1.1 must be confirmed by investigator and/or radiologist before enrollment.

^EThe investigator, or other qualified designee, will provide participants, as well caregiver or family member (if needed), with training and instruction on how to operate the Optune® device for continuous at-home treatment.

^FAny additional on-study hematological and biochemical assessments will only be performed per physician's discretion, if clinically indicated.

^G For persons of reproductive potential, a urine pregnancy test should be performed within 72 hours prior start of trial treatment. Persons will be asked pregnancy status thereafter at the beginning of every treatment cycle. If persons are unsure, then a urine pregnancy test will be performed within 72 hours prior to the next trial cycle. If urine pregnancy results cannot be confirmed as negative, a serum pregnancy test performed by the local study site laboratory will be required. Pregnancy tests (serum and/or urine tests) should be repeated, if required, per institutional guidelines.

^H AEs and laboratory safety measurements will be graded per NCI CTCAE version 4.03. All AEs, whether gradable by CTCAE or not, will also be evaluated for seriousness. Record all AEs occurring within 30 days after the last trial treatment. Report all SAEs (related and unrelated to trial treatment) occurring up until 90 days after the last dose of trial treatment, or the start of new anti-cancer treatment, whichever comes first.

Afterwards, report only SAEs that are related to trial treatment.

^I QoL assessments will be administered before start of treatment (baseline), at 28 weeks, and again at end of treatment (12 months).

^J All participants will be followed for survival status following TTField therapy discontinuation at 6, 12, 24, 36, and 60 months.

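### Contradictory AE recording rules: Section 9.5 can be read to stop recording non-serious device-related AEs at an undefined new therapy while the device is still worn

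*Combined protocol and SAP*

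**What the plan says.** Section 9.5 contains both sides of the conflict. Its window sentence has the investigator record reportable events, starting at consent, with two possible end points. The first is 7 days (AEs) or 30 days (SAEs) beyond the end of participation. The second can come sooner: recording runs only "until the participant receives alternative therapy for his/her SCLC, whichever occurs first". The next sentence keeps SAEs reportable after that point only if they are judged related to study treatment. Non-serious AEs have no such exception. Yet the same section also says "All AEs including local and systemic reactions not meeting the criteria for SAEs will be captured on the appropriate CRF". Further on it adds a second general rule: "All AEs occurring while on study must be documented appropriately regardless of relationship".

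Other sections set no therapy-based stop on AE recording:

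- Section 7.1 (Adverse Event Evaluation) requires serious and non-serious AEs to be recorded, up to 3 months after TTFields ends.
- Section 7.5: "All AEs that occur prior to the EOT visit should be recorded".
- Section 7.8, footnote H: "Record all AEs occurring within 30 days after the last trial treatment".
- Section 9.2 describes AEs, in general terms, as running "from the time of signing the informed consent to completion of the study". This is a definition rather than a recording rule.

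Sections 3.1, 6.3 and 6.6 let a participant start chemotherapy, immunotherapy or radiotherapy and stay on the device to month 12. Section 3.2 makes the incidence of TTFields-related AEs, from start of TTFields to 12 months, a secondary endpoint. Section 10.2 estimates it with an exact confidence interval in the safety set, which Section 10.1 defines as everyone who started the device.

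**The concern.** If alternative therapy means any new anticancer therapy, the cut can fall while the participant is still wearing the device. After it, a non-serious device-related event need not be recorded, but the participant stays in the denominator. A participant whose first related AE is such an event counts as event-free. Repeat events, event types that appear later and worsening grades would also drop out of the AE tables.

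This matters because the expected device toxicity is mostly non-serious. Section 9.4 names dermatitis as the most frequent reaction, and the background studies in Section 1.2 describe it as mild to moderate. Safety is one of the study's stated purposes (Section 3.1), and four sites have no text that tells them which rule governs.

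**Working it through.** **Step 1. The rules side by side.**

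| Place | AE recording ends | Cut at new therapy? |
|---|---|---|
| 9.5, window sentence | 7 days (AE) or 30 days (SAE) after last day of participation | Yes, for AEs and SAEs; related SAEs still reported |
| 9.5, two other sentences | All AEs; all AEs while on study | No |
| 7.1 | 3 months after TTFields completion | No |
| 7.5 | EOT visit | No for recording; follow-up of AEs above Grade 1 may stop |
| 7.8, footnote H | 30 days (AE) or 90 days (SAE) after last treatment | No for AEs; yes for SAEs, related SAEs still reported |

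Only the 9.5 window sentence can remove a device-related AE because other therapy has started. Footnote H's cut removes only SAEs judged unrelated, which are not part of the endpoint.

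**Step 2. Who could be lost.** A participant is lost from the incidence only if all of these hold: new anticancer therapy starts during device wear; the site reads the term as any new anticancer therapy and applies the window sentence over the others; no related AE was recorded before the cut; a non-serious related AE occurs after it, during wear; and no related SAE follows. Removing such a participant lowers the numerator and leaves the denominator unchanged, so the bias cannot be upward.

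**Step 3. Size.** The plan gives no expected AE rate, no rate of later therapy and no safety precision target, so there is no planned figure to reproduce. Every input below is an assumption.

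Let p be the true 12-month incidence of a first non-serious related AE without device exit: 30%, 50% or 80%. For context, Section 1.2 reports dermatitis in 14 of 42 (33%, torso arrays), 8 of 10 (80%) and 10 of 10 (100%). Time to new therapy is exponential with median 3, 6 or 12 months (hazard b = ln 2/median). Device exit is either absent or exponential with median 6 months (hazard d). With constant AE hazard a = −ln(1 − p)/12:

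Loss = a/(a+d) × [1 − e^(−12(a+d))] − a/(a+b+d) × [1 − e^(−12(a+b+d))]

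- Largest cell (p = 80%, median 3 months to therapy, no exit): a = 0.1341, b = 0.2310. Loss = 0.800 − 0.363 = 0.437.
- Middle cell (p = 50%, median 6 months to therapy, median exit 6 months): a = 0.0578, b = d = 0.1155. Loss = 0.292 − 0.194 = 0.098.

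The early-onset rows use the same formula in two pieces, with 80% of first events in month 1. Percentage points lost for median time to therapy of 3/6/12 months:

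| Device exit | Onset | p = 30% | p = 50% | p = 80% |
|---|---|---|---|---|
| None | Constant hazard | 19/13/8 | 31/21/12.5 | 44/29/17 |
| None | Early | 7/4/2 | 11/7/4 | 17/10/6 |
| Median 6 months | Constant hazard | 9/6/4 | 15/10/6 | 23/15/8.5 |
| Median 6 months | Early | 4/2/1 | 7/4/2 | 11/6/3 |

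**Step 4. A second model.** Let a share q start new therapy at month t and stay on the device. Recorded incidence = (1 − q)p + q(1 − e^(−at)). With p = 50%, q = 40%, t = 4: 0.300 + 0.4 × 0.206 = 0.383, a shortfall of 11.7 points, or about 12 of 106. Over p = 30–80%, q = 20–60% and t = 2–6 months, the shortfall runs from 2.7 to 33.9 points.

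Both models assume that every site applies the cut, and both ignore participants recaptured through a later related SAE. Given their inputs, they are therefore upper bounds. If half the participants are at sites applying the cut, the loss halves.

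**The case against.** The case that little or nothing is lost is substantial.

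- *The replacement reading is at least as natural.* Where the protocol means any new anticancer treatment, Section 7.5 and footnote H say so in those terms. Permitted concurrent treatment is listed by type and never called alternative therapy. The clause sits beside windows that start when participation ends, and the next sentence refers to a current treating physician, which fits someone who has left study care. The sentence also speaks of reportable events, although it then names AEs explicitly. Against this, the two parallel new-therapy cuts make the broader reading an easy one for a site to adopt.
- *Several passages require full recording.* A site must set aside Section 7.1, Section 7.5, footnote H and two sentences of Section 9.5. The investigator also asks about AEs at each visit. This makes loss avoidable, but it does not remove the contradiction.
- *Exposure may be small.* The schematic text and Section 6.1 end device treatment at disease progression. If they govern, the overlap is confined to therapy given without progression.
- *First events may come early.* The GBM pilots saw dermatitis after the first treatment course, though they do not fix its timing further. If every first related AE precedes new therapy, the participant-level loss is zero.
- *Consequences are limited.* The endpoint is a secondary estimate with no test or threshold. The stopping rules in Section 9.7 rest on grade 4 toxicity and death, and related SAEs stay reportable.

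These points narrow the concern to a conditional one. They do not answer the undefined term or the conflicting instructions.

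**Conclusion.** The contradiction stands, and the wording should be corrected. If alternative therapy is read as any new anticancer therapy and the 9.5 window sentence is applied, the 12-month incidence of TTFields-related AEs can only be biased downward. There is no loss under the replacement reading, where the other AE passages are followed, or in participant-level incidence for anyone with an earlier related AE or a later related SAE.

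The size is unknown. The modelled range is about 1 to 44 points, or 1 to 23 with median device exit at 6 months. It rests wholly on assumptions and does not show that the effect is material. The 44-point end needs 80% incidence, constant hazard, a 3-month median to new therapy and no device exit, including by death. That is unlikely in extensive-stage disease, where Section 1.1 gives median survival of 9 to 10 months from diagnosis.

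A reader might go further in three ways that the documents do not support:

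- *The incidence will be understated.* This needs both the broader reading and a site choosing that sentence over the others.
- *Device-related SAEs are lost.* Both Section 9.5 and footnote H keep related SAEs reportable after new therapy starts.
- *The other inconsistencies bias the endpoint.* The post-treatment windows and their anchor dates conflict, since Section 4.7 ends participation when follow-up is completed, not when treatment ends. Follow-up of open AEs may stop at new therapy in Section 7.5 but not in Section 9.1, and Section 9.5 says "All AEs will be followed to adequate resolution". CTCAE is 4.03 in footnote H, 5.03 in Section 7.1 and 5.0 in Sections 9.2 and 9.5. All need reconciling, but none is shown to bias the 12-month incidence.

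**What to change.** In Section 9.5 and footnote H, state: *From consent through the last day of device use, all AEs and SAEs are recorded whether or not new anticancer therapy has started. Any new-therapy cut-off applies only to the follow-up window after the last day of device use.*

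Then:

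- Define alternative therapy, or replace it with the term already used in Section 7.5 and footnote H.
- Reconcile Sections 7.1, 7.5, 7.8, 9.1, 9.2 and 9.5 to one AE window, one SAE window, one anchor date, one follow-up rule for open AEs and one CTCAE version.
- Tabulate AEs before and after the start of new therapy.

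Separately, the passages on continuing the device after progression must be reconciled: the schematic text and Sections 6.1 and 4.6 against Sections 3.1, 6.3 and 6.6. No view is taken on which is right, and the proposed recording sentence works either way.

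The cost is protocol wording and modest extra AE entry for participants who are already seen or phoned about monthly (Sections 7.4 and 7.8). More AEs attributable to other therapy will appear in the tables. The before/after split and the existing causality grading deal with that.

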9.6 REPORTING PROCEDURES

OHSU IRB REPORTING OF UNANTICIPATED PROBLEMS AND ADVERSE EVENTS

Unanticipated Problems and AEs will be reported to OHSU IRB according to the policies, procedures and guidelines posted on the [OHSU IRB web site](#).

Events that must be reported by the Investigator to the IRB are detailed in the OHSU IRB **Investigator Guidance: Prompt Reporting Requirements (HRP-801)**. At a minimum, events requiring reporting to the IRB include:

- Any new or increased risk related to the research, including AEs or IDE safety reports that require a change to the protocol or consent,
- New FDA black box warning,
- Publications identifying new risks,
- Data Safety Monitoring Board/Committee letters recommending changes or discussing new risks
- Unanticipated adverse device effect
- Unauthorized disclosure of confidential participant information

CENTRAL REPORTING OF ADVERSE EVENTS FOR MULTICENTER STUDIES

A participating site must report an SAE to the institution's local IRB for action as required, as well as to the OHSU coordinating center study team by phone, fax, or email within 24 hours of learning of the event (or as instructed in the protocol, if different). The participating center will send the coordinating center materials regarding the SAE.

The OHSU coordinating center study team will review and submit SAEs to the FDA, OHSU IRB, and any other required contacts as required by the Knight Data Safety Monitoring Plan (DSMP). The PI at the Coordinating Center is responsible for distributing IND and/or IDE Action Letters or Safety Reports, as applicable, to participating institutions for review and submission to their institution's local IRB.

MEDWATCH REPORTING

The Investigator is required to report AEs to the FDA through the MedWatch reporting program, even if the trial involves a commercially available agent or device. AEs to be reported include any UPs (i.e., not listed in the package insert) and any SAEs with a suspected association to the investigational product.

AEs that occur during clinical studies are to be reported to FDA as specified in the Form FDA 3500, the MedWatch Voluntary Reporting form (available [here](#)), or completed [online](#). A copy of Form FDA 3500 and supporting materials will be kept on file in the study regulatory binder.

MANUFACTURER REPORTING REQUIREMENTS

In the event that a participant experiences an episode of seizure while on study, the investigator or treating physician must report the event to Novocure Inc., and describe the causality relationship of the event to the Optune® Device (refer to Section 9.2.5).

REPORTING OF PREGNANCY

To ensure participant safety, each pregnancy in a participant on study treatment must be reported within 24 hours of learning of its occurrence. The pregnancy should be followed to determine outcome, including spontaneous or voluntary termination, details of the birth, and the presence or absence of any birth defects, congenital abnormalities, or any pregnancy- or childbirth-related and/or newborn complications.

The pregnancy should be recorded on the CRF and reported by the Investigator to Novocure, Inc., as well as any regulatory authority, as needed. Pregnancy follow-up should be reported using the same form. Any SAE experienced during pregnancy must be reported.

